- m Only for patients with enthesitis-related juvenile idiopathic arthritis (ERA) or juvenile psoriatic arthritis (JPsA).
- n Only for patients with JPsA.
- o Only for patients with a history of active or latent TB with documented evidence of appropriate treatment and patients with a positive or repeated not-negative TB test(s) (either PPD, QuantiFERON®-TB Gold, and/or T-SPOT®). A chest x-ray (posterior-anterior view) will be performed at screening unless one has been performed within the past 6 months and the x-ray and reports are available for review.

- p TB tests include PPD, QuantiFERON®-TB Gold, and T SPOT®. In countries where the QuantiFERON-TB Gold test or T-SPOT is available, either test may be used instead of the PPD TB test. The QuantiFERON-TB Gold test may be performed locally or centrally; the T-SPOT must be performed locally. PPD tests must be read 48 to 72 hours after screening. (Note: Exception: Patients with a history of active or latent TB who have documented evidence of appropriate treatment, have no history of re-exposure since their treatment was completed, and have a screening chest x-ray with no evidence of active TB may be enrolled if other entry criteria are met. Such patients would not be required to undergo the protocol-specific TB testing but must have a chest x-ray at screening.)
- q An ECG performed within 1 year prior to screening may be used.
- r Performed locally. To be drawn prior to dosing early in the visit except for V6 and V7.
- s For patients who are positive for HCV antibody, a follow-up test for HCV RNA is required. Patients with a positive HCV antibody will return to the site and have an HCV RNA sample drawn, which will be processed centrally. Results must be known prior to enrollment. Patients who are positive for HCV antibody and negative for HCV RNA may be enrolled.
- t For patients who are positive for hBcAb, a follow-up test for HBV DNA is required. Patients with a positive hBcAb will return to the site and have an HBV DNA sample drawn, which will be processed centrally (for patients in Japan, it is acceptable for sites to draw HBV DNA samples with the test of Visit 1). Results must be known prior to enrollment. Any enrolled patient who is hBcAb positive, regardless of hBsAb status or level, must undergo HBV DNA testing per the schedule of events.
- u Pregnancy tests prior to first dose of investigational product for females ≥ 10 years old of age (< 10 years at investigator discretion) if menarche reached or if there is reason to believe the patient is sexually active. Pregnancy test results from Visit 5 must be known prior to first dose of investigational product.
- v Clinical chemistry will include eGFR (calculated by Bedside Schwartz 2009 formula or the Japanese Society for Pediatric Nephrology formula for patients in Japan).
- w Fasting lipid profile: Patients should not eat or drink anything except water for 4-12 hours depending on weight and age as specified below. If a patient attends these visits in a nonfasting state, this will not be considered a protocol violation. Recommended fasting times by age and weight are as follows:
- Patients ≥ 12 years: fast for 12 hours prior to laboratory test
 - Patients 8 to < 12 years and weighing > 50 kg: fast for 12 hours prior to laboratory test
 - Patients 8 to < 12 years and weighing ≤ 50 kg: fast for 8 hours prior to laboratory test
 - Children < 8 years and weighing 25 to ≤ 50 kg: fast for 8 hours prior to laboratory test
 - Children < 8 years and weighing 10 to < 25 kg: fast for 6 hours prior to laboratory test
 - Children < 8 years and weighing < 10 kg: fast for 4 hours prior to laboratory test
- x Patients in the age cohort of age 2 to ≤ 7 years will not have flow cytometry testing due to blood volume limitations.
- y If patients are eligible for vaccination with tetanus, diphtheria, and pertussis (tDaP) and/or pneumococcal conjugate vaccine according to local recommended schedule of vaccination, IgG titers for eligible vaccine will be evaluated at pre-vaccination, 4 weeks post vaccination, and 12 weeks post vaccination.
- z Estradiol (for females) or testosterone (for males) will be collected for the assessment of pubertal development in patients aged 8 to < 18 years.
- aa PK samples will be collected as described in Sections 9.5.2 and 9.5.3.
- NOTE: Due to blood volume restrictions, some laboratory tests may not be collected. Laboratory samples are recommended to be collected as described in the sponsor-provided weight-based prioritization chart in [Appendix 6](#).

3. Introduction

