IGF-1 and IGFBP-3			X				X								X	X	X
Gonadal hormone ^z			X				X								X	X	X
Exploratory storage samples (RNA, serum, and plasma)			X			X	X								X		
Pharmacogenetic (DNA) collection							X										
PK sample ^{aa}			X	X	X	X	X									X	

Abbreviations: Ab = antibody; ACPA = anti-citrullinated protein antibodies; CHQ-PF50 = Child Health Questionnaire-Parent Form 50;

DNA = deoxyribonucleic acid; DBW = double-blind withdrawal; ECG = electrocardiogram; eCOA = electronic Clinical Outcome Assessment;

eGFR = estimated glomerular filtration rate; EQ-5D-Y = European Quality of Life-5 Dimensions-Youth version; ERA = enthesitis-related juvenile idiopathic arthritis; ESR = erythrocyte sedimentation rate; ETV = early termination visit; hBcAb = hepatitis B core antibody; hBsAb = hepatitis B surface antibody;

hBsAg = hepatitis B surface antigen; HBV = hepatitis B virus; = hepatitis C virus; HIV = human immunodeficiency virus; HLA-B27 = human leukocyte antigen-B27; hsCRP = high-sensitivity C-reactive protein; ICF = informed consent form; IgA = immunoglobulin A; IgG = immunoglobulin G;

IgM = immunoglobulin M; IGF-1 = insulin-like growth factor-1; IGFBP-3 = insulin-like growth factor-binding protein-3; ILAR = International League of

Associations for Rheumatology; IWRS = interactive web-response system; JIA = juvenile idiopathic arthritis; JPsA = juvenile psoriatic arthritis; NK = natural killer; OLLI = open-label lead-in; PASI = Psoriasis Area and Severity Index; PedACR30 = Pediatric American College of Rheumatology 30 criteria; PK = pharmacokinetic(s); PPD = purified protein derivative; RF = rheumatoid factor; RNA = ribonucleic acid; SPARCC = Spondyloarthritis Research Consortium of Canada; TB = tuberculosis; tDaP = tetanus, diphtheria, and pertussis ; TIBC = total iron-binding capacity; TSH = thyroid-stimulating hormone; V = visit; W = week.

- a The OLLI period ends on the same day the DBW period begins.
- b Pharmacokinetic samples will be collected as described in Sections 9.5.2 and 9.5.3. Other baseline laboratory samples should be taken **before** administration of investigational product. Visit 5 (Day 1) will be used as the baseline for OLLI population. Safety/PK cohort will join the OLLI period at Visit 6. The actual study week and study day for the Safety/PK cohort are two weeks longer than that shown due to the additional 2-week safety/PK lead-in assessment period described in [Table JAHV.1](#).

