- c Early termination visit (ETV) occurs if the patient does not have a PedACR30 response rate at Week 12, experiences a flare during the double-blind withdrawal (DBW) (and are not moving to the open-label extension), or terminates participation early. If the ET occurs on the same day as the scheduled visit, any assessments/procedures conducted during the scheduled visit should not be repeated for a separate ETV.
- d Patients who complete the study or discontinue early from the study will have a post-treatment safety follow-up visit (V801) approximately 28 days after the last dose of investigational product. This applies only to patients who do not enter the Open-Label Extension Study.
- e This is the first day of taking the investigational product. .
- f The parent or legal guardian will sign the informed consent form (ICF) and the patient will sign the assent form (as applicable) per local requirements prior to any study assessments, examinations, or procedures being performed.
- g One complete physical examination (excluding pelvic and rectal examinations) will be performed at Visit 1. All subsequent physical examinations may be symptom-directed. A complete physical examination may be repeated at the investigator's discretion at any time. Must include an assessment of serositis, splenomegaly, hepatomegaly, or generalized lymphadenopathy attributable to JIA.
- h Semiannual wrist, hand, finger, and knee radiographs to monitor bone age and long bone growth. Imaging will be required until skeletal maturity is attained, and this should be determined by a qualified physician at the site. For patients already enrolled in JAHV at the time of this amendment, the x-ray procedures will be optional. For these ongoing patients that consent to the x-ray procedures, x-rays must be completed within 30 days from time of consent/assent and every 6 months \pm 30 days thereafter.
- i All patients with active uveitis must be excluded at screening. Signs and symptoms of active uveitis should be monitored. Patients with ERA and JPsA may have a higher risk of active uveitis so mandatory evaluation is required at W12 (V9), W44 (V17), ETV, and V801.
- j Study drug should not be dispensed before review of the Trial Manager report.
- k Patients will return all investigational products for drug accountability.
- l Patient-reported questionnaires will be administered via an on-site eCOA device or paper and is recommended to be completed prior to any clinical examinations.

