5.1.5. Post-Treatment Follow-Up Period

Patients who complete the study or discontinue early from the study will return for the post-treatment safety follow-up visit (Visit 801) approximately 28 days after the last dose of investigational product. Patients who enroll in the OLE study (JAHX) do not need to return for a follow-up visit.

Patients who have received at least 1 dose of investigational product, do not have a PedACR30 response rate at Week 12, experience a flare leading to discontinuation during the DBW (and are not moving to the OLE), or terminate participation early must have an early termination visit (ETV).

Patients who have discontinued investigational product but remain in the study for more than 28 days without investigational product will have an ETV if they chose to withdraw from the study; however, a separate follow-up visit (Visit 801) is not required.

Patients should not initiate new treatment during the post-treatment follow-up period. However, if patients or investigators must initiate a new treatment, patients should complete a Visit 801 prior to the first dose of the new therapy (if possible).

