9.4.6.2. Growth Monitoring

Height and weight will be measured at baseline and postbaseline for the assessment of physical growth according to the Schedule of Activities (Section 2). Height and weight changes in pediatric patients (both at an individual and group level) will be reviewed by the DMC. Height measurements will be made using a stadiometer

Insulin-like growth factor (IGF)-1, the principal mediator of growth hormone, and IGF-binding protein (IGF-BP)-3, the principal carrier protein for IGF-1, will be collected for the assessment of growth-related disorders. Gonadal hormone (estradiol for females or testosterone for males) will be collected for the assessment of pubertal development with patients 8 to <18 years of age. For each patient, laboratory tests detailed in [Appendix 2](#) should be conducted according to the Schedule of Activities (Section 2).

A semiannual wrist, hand, finger, and knee radiographs to monitor bone age and long-bone growth is required, with an option to consent to this procedure for patients already enrolled in the study.

If a local addendum is in place that specifies another mode of imaging (e.g. MRI instead of x-ray), the local addendum should be followed. Otherwise, the current protocol amendment should be followed with regard to knee x-rays.

Any symptomatic areas of bones/joints will be assessed and investigated as appropriate by study investigators. Any diagnoses made based on symptomatic areas of bones/joints or imaging data will be reported as appropriate (e.g. recorded on eCRF).

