10.1. Sample Size Determination

A total of 128 patients will be randomized in a 1:1 ratio to baricitinib or placebo (64 per treatment arm) in the DBW period. This sample size will provide approximately 80% power to detect the difference in time to disease flare between the 2 treatment groups using a 2-sided test with a significance level of 0.05, assuming that the expected percentages of patients experiencing disease flare in the DBW period are 35% for baricitinib and 60% for placebo and that the dropout rate is no greater than 10% in this period.

It is estimated that 197 patients are required to enter the OLLI period to allow 128 patients to be randomized into the DBW period (assuming that 65% of the patients meet the PedACR30 criteria at the end of the OLLI period). The nonresponder and dropout rate will be monitored during the OLLI period to adjust the overall sample size to ensure that a minimum of 128 patients will be randomized in the DBW. If the PedACR30 response rate during the OLLI period is higher than the assumed rate of 65%, fewer than 197 patients may be required.

The above sample size and power estimates are based on nQuery®+nTerim 4.0.

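### Children who flare before Week 44 and move to the extension have no scheduled post-randomization IGF-1, IGFBP-3 or gonadal hormone value in JAHV, and the gap differs by arm

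*Protocol*

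**What the plan says.** Four provisions of the protocol combine.

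- **Sampling times.** In Table JAHV.2 the rows for "IGF-1 and IGFBP-3" and "Gonadal hormone" are marked at Visit 5, Visit 9 (the day of randomization), Visit 17 (Week 44), ETV and V801. Neither is marked from Visit 10 to Visit 16. After Visit 9, height is marked at Weeks 24, 36 and 44 and at ETV.
- **ETV.** Table JAHV.2 footnote c ties the ETV to a patient who "experiences a flare during the double-blind withdrawal (DBW) (and are not moving to the open-label extension". Section 5.1.5 has the same limit: patients who "experience a flare leading to discontinuation during the DBW (and are not moving to the OLE".
- **V801.** Footnote d says of this visit: "This applies only to patients who do not enter the Open-Label Extension Study". Section 5.1.5 agrees: "Patients who enroll in the OLE study (JAHX) do not need to return for a follow-up visit".
- **Purpose.** Section 9.4.6.2 says that IGF-1 and IGFBP-3 "will be collected for the assessment of growth-related disorders", and assigns estradiol or testosterone to pubertal development at ages 8 to under 18.

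A flare ends participation in JAHV, and the patient may go straight to the extension study JAHX (Section 5.1, Figure JAHV.1 footnote c). Sections 8.1.2 and 8.2 send discontinuing patients back to the Section 2 schedule and so add no sample. On the analysis side, SAP Section 6.1.4 compares continuous laboratory variables between arms in the double-blind withdrawal (DBW) period by ANCOVA.

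**The concern.** Whether a child contributes a post-randomization value for these markers depends on whether that child flared. Flare is the primary endpoint, and the trial is powered on its differing between arms. The missing values are therefore selected on outcome, and more of them fall on placebo. The between-arm laboratory comparison would rest mainly on children who kept their response, and those children form a different fraction of each arm.

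These tests serve growth and puberty safety in a pediatric trial, and the exempted patients are seen in clinic with blood being drawn at the visit where the flare is found. The information is lost through schedule wording alone.

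**Working it through.** **Inputs.** 128 randomized, 64 per arm, and planned rates of "disease flare in the DBW period are 35% for baricitinib and 60% for placebo" (Protocol Section 10.1). DBW visits fall every 4 weeks from Week 16 to Week 44, giving 8 intervals (Table JAHV.2). The share of flaring patients who enter the extension is not in the documents. I show 100% and 80% as assumptions.

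**Reproducing the plan's own figure.** With exponential times, HR = ln(0.65)/ln(0.40) = 0.470, and the mean flare rate is (0.35 + 0.60)/2 = 0.475.
- Freedman: 61 events; 61/0.475 = 128.4 patients, without dropout.
- Schoenfeld: 56 events; 56/0.475/0.9 = 131 patients with 10% dropout. With 128 × 0.9 × 0.475 = 54.7 events, power is 79.7%.

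The stated 128 patients and roughly 80% power reproduce, so 35% and 60% are the operative planning rates.

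**Ceiling: every flare counted, all enter the extension.**
- Baricitinib: 0.35 × 64 = 22.4
- Placebo: 0.60 × 64 = 38.4
- Total: 60.8/128 = 47.5%

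**Flares found at Week 44 removed.** Visit 17 is itself a sampling visit, so a flare found there leaves no gap. With a constant hazard, the probability of flare in the first 7 of 8 intervals is 1 − (1 − p)^(7/8).
- Baricitinib: 1 − 0.65^(7/8) = 31.4%, or 20.1 patients
- Placebo: 1 − 0.40^(7/8) = 55.1%, or 35.3 patients

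| Extension uptake (assumed) | Baricitinib without value | Placebo without value | All randomized | Gap between arms |
|---|---|---|---|---|
| 100% | 31.4% | 55.1% | 55.4/128 = 43.3% | 23.7 points |
| 80% | 25.1% | 44.1% | 44.3/128 = 34.6% | 19.0 points |

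At full uptake, values remain for 64 − 20.1 ≈ 44 baricitinib and 64 − 35.3 ≈ 29 placebo patients. Patients who stop without a flare do have an ETV, so dropout itself does not add to this gap.

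**Height.** A flare at Week 16 or 20 precedes the first DBW height at Week 24. On the same hazard assumption this is 2 of 8 intervals: 1 − 0.65^(2/8) = 10.2% on baricitinib and 1 − 0.40^(2/8) = 20.5% on placebo, at full uptake.

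**Base for gonadal hormones.** Only children aged 8 to under 18 are sampled, and Appendix 6 drops the test below 18 kg. The age and weight mix is not given, so the counts above apply to IGF-1/IGFBP-3; for the hormones only the percentages carry over, within the eligible group and if flare rates there match the plan.

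**The case against.** Several points on the other side are sound.

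- **Size.** A reader might infer that about half of all randomized children will lack these values. The documents do not support that. The 47.5% needs full extension uptake and no flare found at Week 44, and for gonadal hormones the base is not all randomized children.
- **Analysis.** The SAP names no analysis of IGF-1, IGFBP-3 or gonadal hormones. Its growth analysis (Section 6.18.4.1) uses weight, height and BMI, and Section 6.18 treats safety p-values as flags only. What is affected is the general laboratory comparison.
- **Growth monitoring.** Weight is taken at every DBW visit, height at three of them, and radiographs are semiannual (optional for patients enrolled before the amendment). A reader should not conclude that growth goes unobserved.
- **JAHX.** The extension may sample at entry. Its schedule is not in these documents, so the gap is established for JAHV only.
- **Limits of a remedy.** Flaring patients leave by design, so follow-up stays shorter on placebo whatever is sampled. SAP Section 6.1 also maps early termination data to the next scheduled visit and summarizes by visit only where the measure was due, so a flare-visit value would not appear in by-visit tables.
- **Stored samples.** A reader might infer that no patient who lost response has an exploratory stored sample. That does not follow: flares found at Week 44 coincide with the Visit 17 sample. Those samples also carry no ETV mark for anyone, so the extension exemption does not cause their absence.

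One counter-reading fails. A flaring patient does end participation early, which is a separate ETV trigger, but applying it here would empty the explicit exception in both footnote c and Section 5.1.5.

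**Conclusion.** The gap is real and explicit, and matching wording in two places makes a slip unlikely. Within JAHV, a child who flares before Week 44 and enters the extension has no scheduled post-randomization IGF-1/IGFBP-3 value, no gonadal hormone value where eligible, and no height if the flare precedes Week 24. The best planning range is about 35% to 43% of randomized patients, with 47.5% as the ceiling and an arm difference of roughly 19 to 24 points. This rests on the protocol's flare rates, a constant hazard, and an assumed uptake of 80% to 100%.

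The consequence is moderate: a laboratory safety comparison with missingness tied to the primary endpoint, and thinner growth monitoring. It does not touch the primary analysis. It merits a change because the change is easy.

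**What to change.** - In footnote c and Section 5.1.5, require IGF-1/IGFBP-3, gonadal hormones where applicable, and height at the flare visit for every DBW flare, including patients moving to JAHX. Footnote c already prevents same-day duplication.
- If JAHX entry already collects these before its first dose, do not draw twice. Name those values in the protocol and SAP as the JAHV end-of-DBW values.
- State in the SAP that these values enter the last-observation and treatment-emergent laboratory analyses, since the by-visit tables will not show them.
- Report the number with a missing post-randomization value by arm. This can also be done for patients who have already left after a flare.

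The cost is schedule wording and a small extra blood volume at a visit where chemistry, hematology and ESR are already drawn. Appendix 6 limits gonadal hormone sampling by age and weight but does not list IGF-1, so that added volume should be checked for the smallest children. The change would leave the unequal length of follow-up between arms as it is, and the report should say so. No change to exploratory storage sampling is proposed.

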3.1. Study Rationale

Baricitinib belongs to the pharmacological class of Janus kinase (JAK) inhibitors. Janus kinases are a family of 4 protein tyrosine kinases (JAK1, JAK2, JAK3, and tyrosine kinase 2 [TYK2]) that play an important role in cytokine signal transduction. Baricitinib is a JAK1/JAK2 inhibitor demonstrating selectivity for and inhibition of JAK1 and JAK2 with lower potency towards inhibition of JAK3 or TYK2 (Fridman et al. 2010).

In isolated enzyme assays, baricitinib inhibited the activities of JAK1, JAK2, TYK2, and JAK3 with half-maximal inhibitory concentration values of 5.9, 5.7, 53, and >400 nM, respectively (Fridman et al. 2010). Janus kinases are enzymes that transduce intracellular signals from cell surface receptors for a number of cytokines and growth factors involved in hematopoiesis, inflammation, and immune function (e.g., interleukin [IL]-2, IL-6, IL-12, IL-15, IL-23, interferons, and granulocyte-macrophage colony-stimulating factor signal through the JAK family) (O'Shea et al. 2015). Within the intracellular signaling pathway, JAKs phosphorylate and activate signal transducers and activators of transcription (STATs), which activate gene expression within the cell. Baricitinib modulates these signaling pathways by partially inhibiting JAK1 and JAK2 enzymatic activity, then reducing the phosphorylation and activation of STATs and thereby reducing inflammation, cellular activation, and proliferation of key immune cells (O'Shea et al. 2013).

The etiology and pathogenesis of juvenile idiopathic arthritis (JIA) are still poorly understood, but JIA shares several immunological abnormalities identified in rheumatoid arthritis (RA) (Ravelli and Martini 2007). The inflammatory synovitis in JIA is similar to that observed in RA. The synovium in JIA shows pronounced hyperplasia of the lining layer and an infiltration of the sublining layer with mononuclear cells, including T cells, B cells, macrophages, dendritic cells, and plasma cells, as similarly observed in RA. Some studies have shown that levels of inflammatory cytokines elevated in adults with RA, such as IL-1 β , IL-6, and tumor necrosis factor-alpha (TNF α), are also elevated in the synovial fluid and serum of patients with JIA. These cytokines also correlate with markers of disease activity such as C-reactive protein (CRP) and erythrocyte sedimentation rate (ESR) (Lepore et al. 1994; Mangge et al. 1995; Rooney et al. 1995, 2000; De Benedetti et al. 1997).

Inflammatory cytokines, such as IL-6, which transduces cell signaling through the JAK/STAT pathway (Rawlings et al. 2004), and TNF, whose expression is reduced by inhibition of JAK1 and JAK2, are considered to be associated with the pathology of JIA (Ravelli and Martini 2007). Pharmacologic interventions that target specific pathways may provide novel therapeutic approaches to disease management for JIA.

The primary treatments in JIA include nonsteroidal anti-inflammatory drugs (NSAIDs), intra-articular and systemic corticosteroids, methotrexate (MTX), and other conventional disease-modifying antirheumatic drug (cDMARDs) (Ringold et al. 2013). Biologic agents developed in the past 20 years have improved the treatments available to children with JIA.

Although these biological treatments led to significant improvements, many patients fail to respond and do not achieve long-lasting remission (Hinze et al. 2015).

Inhibition of JAK-STAT signaling by baricitinib can target multiple JIA-associated cytokine pathways and may provide novel therapeutic approaches to disease management. Baricitinib has demonstrated clinical safety and efficacy in patients with RA in 4 completed Phase 3 studies (Taylor et al. 2017; Genovese et al. 2016; Dougados et al. 2017; Fleischmann et al. 2017) and is approved in the European Union, Japan, and other geographical regions for the treatment of adult patients with moderate-to-severe RA. The rationale for the current study is to evaluate the efficacy and safety of baricitinib when administered once daily (QD) to patients with JIA who have had an inadequate response to either conventional or biologic DMARDs (bDMARDs). The safety and tolerability data from this study are intended to inform the benefit/risk relationship for baricitinib in patients with JIA.

